Figures 4, 5, 6, and 7 show baseline, 4-week, re-evaluation, and final MQH plaque scores. Plaque scores varied throughout the four timepoints with no obvious differences between groups.

[figure not shown]

Figure 5. Baseline MQH scores for A) SRP, B) HP13, and C) HP26

[figure not shown]

Figure 6. 4-Week MQH scores for A) SRP, B) HP13, and C) HP26.

[figure not shown]

Figure 7. Re-Evaluation MQH scores for A) SRP, B) HP13, and C) HP26.

[figure not shown]

Figure 8. Final MQH scores for A) SRP, B) HP13, and C) HP26.

[figure not shown]

Figure 9. Mean BOP in each group, SRP, HP13, and HP26

[figure not shown]

Figure 10. BOP % in pockets initially <5 mm

[figure not shown]

Figure 11. BOP % in pockets initially  $\geq 5$ mm

Figure 8 shows mean BOP. Baseline mean BOP was 45% for SRP, 57% for HP13, and 63.1% for HP26. At 4-weeks, mean BOP was 45% for SRP, 60% for HP13, and 44% for HP26. At re-evaluation, mean BOP was 37% for SRP, 30% for HP13, and 27% for HP26. Final mean BOP scores were 44% for SRP, 33% for HP13, and 28% for HP13. Mean BOP was significantly reduced in all groups between 4-week examination and re-evaluation with mean BOP scores at final examination staying similar to levels at re-evaluation for HP13 and HP26 groups. Mean BOP scores at final examination group for SRP group was similar to baseline.

Figure 9 shows BOP % in pockets initially  $< 5$ mm. At baseline, 24% of pockets  $< 5$ mm were BOP for SRP, 47% for HP13, and 52% for HP26. At 4-week examination BOP % were 29% for SRP, 44% for HP13, and 35% for HP26. At re-evaluation, BOP %

was 27% for SRP, 21% for HP13, and 22% for HP26. At the final exam, BOP % was 33% for SRP, 26% for HP13, and 22% for HP26.

Figure 10 shows BOP % in pockets initially  $\geq 5$ mm. At baseline, BOP % was 92% for SRP, 81% for HP13, and 91% for HP26. At 4-week examination, BOP % was 91% for SRP, 93% for HP13, and 83% for HP26. Re-evaluation BOP % was 91% for SRP, 78% for HP13, and 75% for HP26. At final examination, BOP % was 88% for SRP, 79% for HP13, and 78% for HP26.

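### Bleeding in pockets labelled as initially <5 mm and ≥5 mm does not reconcile with overall bleeding if the strata were fixed at baseline; re-classification by current depth is the most likely cause

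*Combined protocol and SAP*

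**What the plan says.** The Results chapter reports BOP in three ways for each arm and visit: overall, in pockets initially <5 mm, and in pockets initially ≥5 mm. The text introduces the stratified figures with "shows BOP % in pockets initially", and the captions of Figures 10 and 11 carry the same label (the text calls them Figures 9 and 10). The natural meaning is that each site stays in the stratum set by its baseline depth.

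- Whole-mouth bleeding at the start of the study is given as "Baseline mean BOP was 45% for SRP, 57% for HP13, and 63.1% for HP26". The corresponding shallow-stratum values are 24, 47 and 52%.
- The whole-mouth result at week 13 reads "At re-evaluation, mean BOP was 37% for SRP, 30% for HP13, and 27% for HP26", while the deep stratum at that same visit reads "Re-evaluation BOP % was 91% for SRP, 78% for HP13, and 75% for HP26".
- For week 26 the whole-mouth sentence is "Final mean BOP scores were 44% for SRP, 33% for HP13, and 28% for HP13". It names HP13 twice; the last value is read here as HP26.

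No site counts per stratum are given. The Statistical Analysis section names BOP among the primary outcomes (and again among the secondary ones) and summarises it per mouth, but defines no BOP analysis by pocket depth.

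**The concern.** With a fixed set of sites, overall bleeding must be explained by bleeding in the two strata at one unchanging mix. Some reported figures visibly resist this. In SRP from baseline to week 13, overall BOP falls by 8 points (45 to 37), yet the shallow stratum rises by 3 (24 to 27) and the deep stratum falls by only 1 (92 to 91). In HP26 from baseline to week 26, overall BOP falls by 35.1 points (63.1 to 28), more than either stratum (52 to 22, a fall of 30; 91 to 78, a fall of 13). With pooled sites and a constant mix, the overall change must lie between the two stratum changes.

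If sites were re-sorted by current depth at each visit, a pocket that becomes shallow leaves the ≥5 mm group. Figures 10 and 11 would then follow a different set of sites each time and would not show change in the original deep or shallow pockets. A comparison of arms within a stratum would condition on depth after treatment, which treatment may itself have changed.

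**Working it through.** **Inputs** (Results chapter; SRP / HP13 / HP26, in %):

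| Visit | Overall | Shallow (<5 mm) | Deep (≥5 mm) |
|---|---|---|---|
| Baseline | 45 / 57 / 63.1 | 24 / 47 / 52 | 92 / 81 / 91 |
| Week 4 | 45 / 60 / 44 | 29 / 44 / 35 | 91 / 93 / 83 |
| Week 13 | 37 / 30 / 27 | 27 / 21 / 22 | 91 / 78 / 75 |
| Week 26 | 44 / 33 / 28 | 33 / 26 / 22 | 88 / 79 / 78 |

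**Step 1: implied deep share.** For pooled sites, overall = w × deep + (1 − w) × shallow, so w = (overall − shallow) / (deep − shallow). Without site counts, the baseline value has to be solved for, so it reproduces baseline overall BOP by construction. The test is whether the same w fits later visits.

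For HP26, baseline w = (63.1 − 52)/(91 − 52) = 11.1/39 = 28.5%, and week 13 w = (27 − 22)/(75 − 22) = 5/53 = 9.4%. Rounding limits, in brackets, move each input by ±0.5 (63.1 by ±0.05).

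| | Baseline | Week 4 | Week 13 | Week 26 |
|---|---|---|---|---|
| SRP | 30.9 (29.4–32.4) | 25.8 (24.2–27.4) | 15.6 (14.1–17.2) | 20.0 (18.2–21.8) |
| HP13 | 29.4 (26.5–32.4) | 32.7 (30.6–34.7) | 15.8 (14.0–17.5) | 13.2 (11.3–15.1) |
| HP26 | 28.5 (27.1–29.9) | 18.8 (16.7–20.8) | 9.4 (7.5–11.3) | 10.7 (8.9–12.5) |

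No single share fits all four visits in any arm, even at the rounding limits. At week 4, HP13 is unchanged within rounding and SRP falls by only about 16% of its baseline share. The case rests on weeks 13 and 26.

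**Step 2: overall BOP if the baseline share held.** Predicted = shallow + w(baseline) × (deep − shallow). For HP26 at week 13 this is 22 + 0.285 × 53 = 37.1.

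| | Week 13 predicted (range) vs reported | Week 26 predicted (range) vs reported |
|---|---|---|
| SRP | 46.8 (45.3–48.2) vs 37 | 50.0 (48.7–51.3) vs 44 |
| HP13 | 37.8 (35.6–39.9) vs 30 | 41.6 (39.5–43.6) vs 33 |
| HP26 | 37.1 (35.8–38.3) vs 27 | 37.9 (36.6–39.2) vs 28 |

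The gaps are 6 to 10 points. With every input rounded in the documents' favour, the smallest is still 48.7 − 44.5 = 4.2 points (SRP, week 26).

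**Step 3: does the share follow current depth?** Reported mean PD (mm) at the four visits is 3.88, 3.67, 3.30, 3.43 in SRP; 4.11, 4.06, 3.43, 3.40 in HP13; and 3.83, 3.55, 3.14, 3.23 in HP26. Over these 12 arm-visits its correlation with the implied share is about 0.96. The two move in the same direction in 8 of 9 intervals; the exception, HP13 to week 4, is within rounding. In SRP the share rises again from week 13 to week 26, beyond rounding, as mean PD rises. The HP26 rise is in the same direction but within rounding. A fixed baseline stratum has no reason to follow current depth; a re-sorted one does.

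**The case against.** The strongest objection is that the identity in Step 1 is strict only for pooled sites, whereas the Statistical Analysis section describes a mean per mouth. If the overall and stratum figures are all patient averages, overall = mean shallow + mean share × mean (deep − shallow) + the between-patient covariance of share and that difference. The baseline share is then also unknown. With a constant HP26 share of 17.5%, the covariances needed are +4.3, +0.6, −4.3 and −3.8 points at the four visits. SRP at 23.5% needs +5.0, +1.4, −5.0, −1.9, and HP13 at 22.5% needs +2.4, +5.0, −3.8, −4.9; rounding lowers the largest in each of these two arms to about 4.0. Assuming, for scale, between-patient SDs of 0.15 for the share and 30 points for the difference, the covariance can reach 0.15 × 30 = 4.5 points. So fixed strata are arithmetically possible, and a reader who infers that they are proved impossible goes too far.

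That route is contrived, however. At these shares the covariance must change sign between week 4 and week 13 in all three arms. In HP26, under the assumed SDs, the correlation would have to swing from about +0.96 to −0.96 (4.3/4.5). The PD standard errors also suggest pooling. An SE of 0.06 mm with 3 patients implies a between-patient SD of only 0.06 × √3 = 0.10 mm, and 0.04 mm with 9 patients implies 0.04 × √9 = 0.12 mm. At a minimum of 20 teeth × 6 sites per patient, the same SEs imply site SDs of 0.06 × √360 = 1.1 mm and 0.04 × √1080 = 1.3 mm, which is more credible. This is an inference from PD, not proof for BOP.

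Second, sites or subjects may have dropped out. Follow Up Care excludes re-treated sites from the final data, and the sex counts in Results sum to 18 against 15 completers. If all shallow sites stayed, the fraction of deep sites lost would be 1 − [w/(1 − w)] / [w₀/(1 − w₀)], where w₀ is the baseline share. That is 59/55/74% by week 13, and 42% in HP26 by week 4, before SRP had begun. Exclusion alone is not a plausible explanation. If it were the cause, the strata would still not be the intact initial sites.

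Third, Results reports no test on these strata, and neither the Discussion nor the Conclusion cites them. That stands.

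**Conclusion.** The stratified and overall BOP figures do not reconcile with strata fixed at baseline. Under pooling, the implied deep share falls by 46 to 67% of its baseline value at week 13 and by 35 to 62% at week 26, and the discrepancy in overall BOP is 6 to 10 points in every arm at both visits. Re-classification by current depth is the most likely cause, but the documents do not establish it. The week-26 HP26 figure depends on reading the second HP13 in the final BOP sentence as HP26; week 13 does not.

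Three stronger inferences are not supported. Fixed strata are very unlikely, not impossible. Nor can one say that only bleeding sites remain in the deep group or that its BOP would stay flat whatever the treatment: 12 to 22% of deep sites do not bleed at week 26, and deep BOP falls by 13 points in HP26 against 4 in SRP. Finally, the Discussion's claim of a bleeding benefit is not shown to rest on these strata. If sites were re-classified, the within-stratum arm comparison conditions on a post-treatment outcome, but the size of any resulting bias cannot be derived from what is reported.

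**What to change.** Recompute both strata with each site's membership fixed by its baseline PD (<5 or ≥5 mm), and report the number of sites and patients per stratum, arm and visit. State whether the overall and stratum percentages are pooled over sites or averaged per mouth, and correct the arm label in the final BOP sentence. If the current figures were built on depth at each visit, either replace them or relabel them as BOP by current depth, with a note that they do not show change from baseline. With 3, 3 and 9 patients this can stay descriptive; no added between-arm test is needed. The cost is one re-tabulation of data already collected, plus corrected text and two figures.

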## CHAPTER FOUR

### DISCUSSION

This randomized, examiner-blind, parallel-design, clinical trial compared the effectiveness of SRP to daily treatment with 1.7% hydrogen peroxide using prescription, custom-fabricated dental trays as an adjunct to SRP. The results of this study demonstrate that the peroxide/prescription tray treatment regimen in combination with SRP is statistically significant in terms of reduction of BoP

In contrast to prior studies (Putt 2012, 2013 Journal of Clinical Dentistry), this study did not provide evidence to show that the use of peroxide/prescription tray regimen prior to SRP would reduce pocket depths without mechanical intervention. According to Putt 2012, the mean difference between test and control group after two weeks of 4-times daily use hydrogen peroxide was 0.44 mm in sites >5mm. The difference between test and control groups for all sites was 0.18mm. The difference that was seen between our study was that the subjects were instructed to use twice daily hydrogen peroxide, therefore the total “contact time” of peroxide is effective half.

The amount of marginal tissue recession over time did not demonstrate an increase of soft tissue recession over time with the use of the prescription trays indicated that the physical seal along the gingival margin does not induce or propagate recession.

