## **Exclusion Criteria**

- 1) Any systemic conditions or medication intake that can alter periodontal status (e.g. uncontrolled diabetes (with <3-month recent HbA1c of  $>8.5\%$ ), anti-seizure medication, immunosuppressant, and calcium channel blockers with clinical sign of gingival overgrowth.
- 2) Immune-compromised state.

- 3) Any current heavy smoking habits (>10 cigarettes/day)
- 4) Any medical condition or history requiring prophylactic antibiotic coverage prior to dental treatment.
- 5) Females who are lactating or pregnant (as determined by medical history) or planning to become pregnant for the duration of the study.
- 7) Physical limitations/restrictions compromising oral hygiene procedures.
- 8) The presence of significant oral soft tissue pathology and/or lesions associated with ill-fitting appliances or restorations.
- 9) Tooth mobility associated with advanced periodontal disease (e.g. score of >2 using Miller Classification).
- 10) Any temporomandibular joint disorders.
- 11) Grossly carious, orthodontically banded, and third molars will not be included in the tooth count.
- 12) Presence of any significantly tipped, crowded, or largely defective restorations.
- 13) Any extreme adverse events relating to the use of HP gel (e.g. prolonged tooth hypersensitivity or aberrant soft tissue/mucosal reaction)

All participants were screened and evaluated at Loma Linda University School of Dentistry Graduate Periodontics Department. There are three groups of 20 patients, two therapy test groups and the control group.

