### **Therapy Phase**

The therapy phase consisted of establishing baseline periodontal parameters and implementation of standardized oral hygiene instructions. All subjects were given verbal and visual instructions and demonstrated whether or not they can perform adequate oral hygiene with repeated instructional sessions throughout the study (see Fig. 1). Oral hygiene instructions (OHI) included use of plaque disclosing agent and proper use of indicated oral hygiene aids. The remaining areas of disclosed plaque assessed the quality of oral hygiene. Subjects in the two therapy test groups were given their customized prescription tray along with supervised instructions during their first try-in. The therapy consisted of initiation of 1.7% HP gel delivered in these customized trays (Perio Protect Tray, Perio Protect, LLC, St. Louis, MO, USA) four weeks prior to non-surgical periodontal treatment, SRP, at week 0. Subjects were instructed to deliver the gel 2-times daily for 15 minutes. These subjects also received calendar journals and will be asked to log entries of when they have used their trays.

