## **Statistical Analysis**

The primary outcome variables are PD reduction, RAL gain, and reduction in BOP. PD data was computed to provide a mean score per mouth. Secondary efficacy variables were BOP, and MQH. BOP was computed to provide a mean score per mouth for each clinical assessment and were analyzed using repeated measures (ANOVA). Outcome variable data analysis consisted of between-treatment and within-treatment (longitudinal) comparisons of PD and CAL at all examination time points using parametric procedures. Between-treatment and within-treatment comparisons employed baseline data and analysis of covariance (ANCOVA) for follow-up data. All comparisons were performed using two-sided hypothesis tests, and employed a 0.05 level of significance.

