## CHAPTER THREE

### RESULTS

There were total 15 subjects who completed the 6-month trial. There were 10 males with an mean age of 55.6 years and 8 males with an mean age of 51.1 years. There was a total of 3 patients in SRP group, 3 patients in HP13 group, and 9 patients in HP26 group. The mean pocket depth (PD) shown in figure 1 at baseline for SRP group was  $3.88 \pm 0.06$  mm (std. error),  $4.11 \pm 0.06$  mm for HP13, and  $3.83 \pm 0.04$  mm for HP26. At the 4-week examination, PD for SRP group decreased to  $3.67 \pm 0.06$  mm,  $4.06 \pm 0.06$  mm with HP13, and  $3.55 \pm 0.04$  mm for HP26. At the re-evaluation examination, PD for SRP group was  $3.30 \pm 0.06$  mm,  $3.43 \pm 0.06$  mm for HP13, and  $3.14 \pm 0.04$  mm for HP26. The final examination, PD were  $3.43 \pm 0.06$  for SRP,  $3.40 \pm 0.06$  mm for HP 13, and  $3.23 \pm 0.04$  mm for HP26. Repeated measure ANOVA showed significant difference in pocket depth among all time points in all treatment groups. In SRP group, no significant difference between baseline and 4 weeks in pocket depth and relative attachment level.

[figure not shown]

Figure 2. Mean PD in each group, SRP, HP13, and HP26.

Figure 2 shows the mean relative recession over time. The mean relative recession at baseline was  $3.28 \pm 0.06$  mm for SRP,  $2.87 \pm 0.06$  mm for HP13, and  $3.21 \pm 0.03$  mm for HP13. At 4-weeks, it was  $3.35 \pm 0.06$  mm for SRP,  $3.23 \pm 0.05$  mm for HP13, and  $3.15 \pm 0.03$  mm for HP26. At re-evaluation it was  $3.33 \pm 0.06$  mm for SRP,  $3.27 \pm 0.05$  mm for HP13, and  $3.29 \pm 0.03$  mm for HP26.

[figure not shown]

Figure 3. Mean R-Rec in each group, SRP, HP13, and HP26.

Figure 3 shows the mean relative attachment level. The mean RAL at baseline was  $7.16 \pm 0.08$  mm for SRP,  $6.97 \pm 0.07$  mm for HP13, and  $7.04 \pm 0.04$  mm for HP26. At 4-weeks, the RAL was  $7.02 \pm 0.08$  mm for SRP,  $7.29 \pm 0.07$  mm for HP13, and  $6.69 \pm 0.05$  mm for HP26. At re-evaluation the RAL was  $6.63 \pm 0.08$  mm for SRP,  $6.15 \pm 0.07$  mm for HP13, and  $6.39 \pm 0.04$  mm for HP26. At the final exam RAL was  $6.79 \pm 0.08$  mm for SRP,  $6.71 \pm 0.07$  mm for HP13, and  $6.53 \pm 0.04$  mm for HP26.

[figure not shown]

Figure 4. Mean RAL in each group, SRP, HP13, and HP26.

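### The Discussion contrasts the week-4 pocket-depth result with an earlier trial and explains it by contact time, but reports no between-group estimate; the result is inconclusive about 0.18 mm unless the patient-level SD is below about 0.12 mm

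*Combined protocol and SAP*

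**What the plan says.** The plan was for 60 patients: "There are three groups of 20 patients, two therapy test groups and the control group". The Statistical Analysis section summarises pocket depth (PD) as a mean per mouth and states that "All comparisons were performed using two-sided hypothesis tests, and employed a 0.05 level of significance". The Results (Chapter Three) give the completers: "There was a total of 3 patients in SRP group, 3 patients in HP13 group, and 9 patients in HP26 group". They print mean PD with standard errors by arm and visit, but no week-4 comparison between gel and SRP.

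The Discussion (Chapter Four) introduces the pre-SRP result as standing apart from previous trials and states that "this study did not provide evidence to show that the use of peroxide/prescription tray regimen prior to SRP would reduce pocket depths". It then cites the earlier trial's test-control difference, which "after two weeks of 4-times daily use hydrogen peroxide was 0.44 mm in sites >5mm", and adds: "The difference between test and control groups for all sites was 0.18mm". It puts the discrepancy down to this trial's twice-daily use, said to halve the total contact time.

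The Abstract and the Conclusion (Chapter Five) say something else: PD and attachment level improved significantly in both gel groups after 4 weeks of tray use, with no significant effect in the SRP group.

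**The concern.** Saying that two trials differ, and then giving a reason, presupposes that they do differ. For that, this trial's interval for the gel effect at week 4 would have to exclude the earlier effect. No such interval is given, and the Discussion mentions neither the size of the control arm nor the precision. A reader may take away that the earlier effect was not reproduced and that the schedule is the reason.

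The Abstract and Conclusion lead to the opposite inference, because they set significance in the gel arms beside non-significance in the SRP arm. That is not a comparison between arms. What the trial can say about gel use before SRP is therefore stated in two incompatible ways, and neither rests on a between-group estimate.

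**Working it through.** The documents give no week-4 between-group figure to reproduce, so the check starts from the printed means.

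**Inputs.** Mean PD (standard error) in mm, from the Results:

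| Arm | n (6-month completers) | Baseline | Week 4 | Change |
|---|---|---|---|---|
| SRP | 3 | 3.88 (0.06) | 3.67 (0.06) | -0.21 |
| HP13 | 3 | 4.11 (0.06) | 4.06 (0.06) | -0.05 |
| HP26 | 9 | 3.83 (0.04) | 3.55 (0.04) | -0.28 |

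HP13 and HP26 follow the same regimen up to week 4, so they can be pooled.

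**Step 1, point estimate.** Pooled gel change = (3 × -0.05 + 9 × -0.28)/12 = -0.2225 mm. Gel minus SRP = -0.2225 + 0.21 = -0.0125 mm (negative favours gel).

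**Step 2, precision.** For 12 versus 3 patients, the half-width is t(0.975, 13 df) × SD × √(1/3 + 1/12) = 2.160 × 0.6455 × SD = 1.39 × SD. The interval excludes a 0.18 mm benefit only if 1.3945 × SD < 0.18 - 0.0125, that is, SD < 0.120 mm.

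**Step 3, range of SD.** The patient-level SD of change is not given, so it is assumed over a range. Power is from the noncentral t, two-sided 0.05:

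| Assumed SD (mm) | 95% CI, gel minus SRP (mm) | Includes -0.18? | Power for 0.18 mm |
|---|---|---|---|
| 0.10 | -0.15 to 0.13 | no | 73% |
| 0.15 | -0.22 to 0.20 | yes | 41% |
| 0.20 | -0.29 to 0.27 | yes | 25% |
| 0.30 | -0.43 to 0.41 | yes | 14% |
| 0.50 | -0.71 to 0.68 | yes | 8% |

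**Step 4, what the printed standard errors imply.** Read as per-mouth, SD = SE × √n:
- SRP and HP13: 0.06 × √3 = 0.10 mm
- HP26: 0.04 × √9 = 0.12 mm

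Read as site-level, with 20 to 28 teeth and six sites each, SD = SE × √(n × teeth × 6) gives about 1.1 to 1.6 mm between sites.

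Taking the per-mouth reading and allowing unequal variances (Satterthwaite t, 3.4 df), the result depends on the assumed baseline/week-4 correlation:
- correlation 0: -0.30 to 0.28 mm
- correlation 0.5: -0.22 to 0.19 mm
- correlation 0.8: -0.14 to 0.12 mm

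**Step 5, an internal benchmark.** HP13 and HP26 differ by 0.28 - 0.05 = 0.23 mm in mean change on the same regimen. At an SD of 0.12 mm the standard error of that gap is 0.12 × √(1/3 + 1/9) = 0.08 mm, so the gap is 2.9 standard errors. An SD that small fits poorly, although three patients make this only suggestive.

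**Step 6, the contact-time explanation.** The earlier regimen, as the Discussion describes it, is 4 per day × 14 days = 56 applications. In this trial, the Therapy Phase section says "Subjects were instructed to deliver the gel 2-times daily for 15 minutes", starting "four weeks prior to non-surgical periodontal treatment, SRP, at week 0": 2 per day × 28 days = 56 applications. Total contact time before SRP is therefore not halved if minutes per application are equal. The earlier trial's minutes are not given.

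**Step 7, the three statements side by side.** The Discussion reports no evidence of a pre-SRP PD reduction; the Abstract and Conclusion report significant PD improvement in both gel groups. The printed means fit neither contrast well: HP13, counted as improved, fell by 0.05 mm, while SRP, called non-significant, fell by 0.21 mm.

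**The case against.** The strongest reply is that saying the study provided no evidence is the right phrasing for an inconclusive result. A reader might infer that the Discussion claims gel has no effect before SRP. It does not, and that sentence can stay. The opening contrast can even be read literally: earlier trials gave evidence and this one did not. That reading does not cover the contact-time sentence, which explains a difference not shown to exist. If daily contact was meant, halving is right for equal minutes, but the text refers to the total.

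A reader might also infer that the trial definitely cannot exclude 0.18 mm. The documents do not support that without a condition. If the standard errors are per-mouth, as the Statistical Analysis section suggests for PD, the pooled SD is √[(2 × 0.0108 + 2 × 0.0108 + 8 × 0.0144)/12] = 0.115 mm. At a correlation of 0.5 the SD of change is the same, and the equal-variance interval then reaches a benefit of 0.0125 + 1.3945 × 0.115 = 0.173 mm, just excluding 0.18 mm. This stands as a possibility. The site-level reading is more plausible, and the gap between the gel arms points to a larger SD.

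Nor do the documents say that three controls were measured at week 4. The 3/3/9 are six-month completers, the subjects described by sex add to 10 + 8 = 18 rather than 15, and the SRP visit schedule lists no week-4 data collection although a week-4 SRP mean is printed.

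Finally, the second primary objective names inflammation rather than PD, so this is not a failure of that objective as worded. The 0.18 mm comes from a different schedule; it serves here only because the Discussion itself uses it as the comparator.

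**Conclusion.** The point holds conditionally. The documents do not support presenting the week-4 PD result as a contrast with the earlier 0.18 mm. The estimate implied by the printed means is about -0.01 mm. With 12 versus 3 patients, the result is inconclusive about 0.18 mm unless the patient-level SD of change is below about 0.12 mm. This rests on the completer counts applying at week 4, on pooling the two gel arms, and on an SD that the documents do not give.

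Two parts need no assumed SD. The claim of halved total contact time conflicts with 56 applications under each schedule, given equal minutes per application. The Discussion also disagrees with the Abstract and Conclusion on week-4 PD. The 0.44 mm figure has no counterpart here, because the readable results give no PD by depth stratum. The matter is worth correcting because it changes what the trial can be said to show before SRP, but it is a fault of inference and reporting and does not show that the gel works or fails.

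**What to change.** 1. Report the week-4 gel-minus-SRP difference in per-mouth PD, adjusted for baseline, with both gel arms pooled, its 95% CI and the number of patients measured at week 4 in each arm. State whether the printed standard errors are per patient or per site.
2. Keep the statement that no evidence was provided, but call the result inconclusive where the interval includes 0.18 mm. Describe it as differing from the earlier trial only if the interval excludes that value.
3. Remove the contact-time explanation. Drop the 0.44 mm comparison unless PD is computed in the same depth stratum.
4. Reconcile the Abstract, Discussion and Conclusion so that the week-4 statement rests on this between-group estimate and not on separate within-group tests.

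The cost is one analysis of data already held and a few reworded sentences. The downside is a less definite statement about gel use before SRP.
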